11.2.5 Safety Analyses

The safety analyses will be performed using the safety population (all patients who have received at least 1 dose of CO-1686).

11.2.5.1 Extent of Exposure

The following will be summarized:

- Number of weeks of treatment initiated
- Number of dose reductions, delays or interruptions

The number of weeks of treatment initiated will be investigated by summarizing the number of weeks started by each patient. The number of patients with at least 1 dose reduction, delay or interruption will be summarized with frequencies and percentages.

11.2.5.2 Adverse Events

AE coding will be performed using MedDRA. The severity of the toxicities will be graded according to the NCI CTCAE v4.03 whenever possible. Treatment-emergent AEs are defined as

AEs with an onset date on or after the date of first dose of CO-1686 until the date of the last CO-1686 dose plus 28 days. AEs will be considered treatment-emergent if all or part of the date of onset of the AE is missing and it cannot be determined if the AE meets the definition for treatment-emergent.

The number and percentage of patients who experienced treatment-emergent AEs for each SOC and PT will be presented. Multiple instances of the treatment-emergent AEs in each SOC and multiple occurrences of the same PT are counted only once per patient. The number and percentage of patients with at least 1 treatment-emergent AE will also be summarized.

Separate tables will present the following:

- All treatment-emergent AEs
- Treatment-emergent AEs by CTCAE grade
- Grade 3 or greater treatment-emergent AEs
- Treatment-related, treatment-emergent AEs
- Serious treatment-emergent AEs
- Treatment-emergent AEs with an outcome of death
- Treatment-emergent AEs leading to discontinuation of PO CO-1686
- Treatment-emergent AEs resulting in interruption or reduction or delay of CO-1686

The incidence of treatment-emergent AEs will be summarized by relationship to PO CO-1686 using “treatment-related” and “not treatment-related” categories. If a patient experiences multiple occurrences of the same AE with different relationship categories, the patient will be counted once as a relationship category of treatment-related.

If a patient experiences multiple occurrences of the same AE with different intensity toxicity grades, the patient will be counted once for the maximum (most severe) toxicity grade. AEs with a missing intensity will be presented in the summary table with a toxicity grade of “Missing.” For each toxicity grade, the number and percentage of patients with at least 1 treatment-emergent AE of the given grade will be summarized.

Non-treatment-emergent AEs (pretreatment and post-treatment) will be presented in the data listings.

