Overall	28 (73.7%)	18 (94.7%)	16 (88.9%)	15 (88.2%)	28 (56.0%)	6 (100.0%)	111 (75.0%)
Gastrointestinal Disorders							
Diarrhea	6 (15.8%)	6 (31.6%)	4 (22.2%)	4 (23.5%)	6 (12.0%)	2 (33.3%)	28 (18.9%)
Nausea	8 (21.1%)	6 (31.6%)	6 (33.3%)	7 (41.2%)	12 (24.0%)	3 (50.0%)	42 (28.4%)
Vomiting	5 (13.2%)	2 (10.5%)	3 (16.7%)	4 (23.5%)	4 (8.0%)	0	18 (12.2%)
General Disorders and Administration Site Conditions							
Fatigue	9 (23.7%)	6 (31.6%)	5 (27.8%)	3 (17.6%)	5 (10.0%)	1 (16.7%)	29 (19.6%)
Investigations							
Electrocardiogram QT prolonged	0	2 (10.5%)	0	2 (11.8%)	5 (10.0%)	3 (50.0%)	12 (8.1%)
Metabolism and Nutrition Disorders							
Combined terms of hyperglycemia	4 (10.5%)	6 (31.6%)	11 (61.1%)	10 (58.8%)	14 (28.0%)	4 (66.7%)	49 (33.1%)
Decreased appetite	1 (2.6%)	6 (31.6%)	4 (22.2%)	3 (17.6%)	2 (4.0%)	2 (33.3%)	18 (12.2%)
Musculoskeletal and Connective Tissue Disorders							
Muscle spasms	3 (7.9%)	4 (21.1%)	3 (16.7%)	0	3 (6.0%)	0	13 (8.8%)
Myalgia	3 (7.9%)	4 (21.1%)	2 (11.1%)	0	1 (2.0%)	1 (16.7%)	11 (7.4%)

Abbreviations: TEAE, treatment-emergent adverse event; BID, twice daily; FB, CO-1686 free base; HBr, CO-1686 hydrobromide; N, number of patients; PT, preferred term; SOC, system organ class.

[figure not shown]

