6 STUDY POPULATION

6.1 Number of Patients and Sites

The total enrollment planned for this study is approximately 225 patients. Patients will be enrolled into 2 cohorts:

Cohort A: Approximately 125 patients with centrally confirmed T790M-positive NSCLC will be enrolled. These patients will be treated at a dose of 625 mg BID.

Cohort B: Approximately 100 patients will be enrolled in order to include approximately 40 response evaluable, centrally confirmed T790M-negative patients. All Cohort B patients will be treated at a dose of 500 mg BID.

The priority for study inclusion will be for all T790M-positive patients to be enrolled into Cohort A first. Once this cohort is complete, eligible T790M-positive patients will then be enrolled into Cohort B. All eligible T790M-negative patients will be enrolled into Cohort B.

There will be approximately 90 investigative sites in the United States (US), Europe, Asia, and Australia.

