7.3 Preparation and Administration of Protocol-specified Treatment

CO-1686 will be administered at a dose of 625 mg BID (Cohort A) or 500 mg BID (Cohort B). Patients should take CO-1686 as directed by the treating physician. Each dose should be taken with 8 oz (240 mL) of water and with a meal or within 30 minutes after a meal. Tablets should be swallowed whole.

If a patient misses a dose (i.e., does not take it within 6 hours of the scheduled time), he or she should resume taking CO-1686 with their next scheduled dose. Missed or vomited doses will not be made up.

The investigator or designee will be responsible for distributing the appropriate strength(s) of PO CO-1686 tablets to all patients. A sufficient number of tablets will be provided to the patient to last until the next scheduled visit. Patients will be instructed to record daily doses taken or not taken on a patient diary, and will be instructed to bring their CO-1686 tablets and patient diary to the next scheduled visit for reconciliation by site personnel.

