11.2 Statistical Methods

11.2.1 General Considerations

Data will be summarized by T790M status and by dose, but may also be pooled as appropriate.

Quantitative variables will be summarized using descriptive statistics (N, mean, standard deviation, median, minimum, and maximum) and/or frequency and percentages for medically relevant categories. Categorical variables will be presented using frequencies and percentages.

Kaplan-Meier methodology will be used to summarize PFS and OS.

All data will be used to their maximum possible extent but without any imputations for missing data.

All statistical analyses will be conducted with the statistical analysis software (SAS®) System.

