#### 11.1 Adverse Events

Adverse events will be classified using the Medical Dictionary version 16.1 for Drug Regulatory Activities (MedDRA) classification system. The severity of the toxicities will be graded according to the NCI CTCAE whenever possible. Treatment-emergent adverse events (TEAEs) are defined as AEs with onset date on or after the date of first dose of study medication until the date of the last study medication dose plus 28 days. Adverse events will be considered treatment-emergent if all or part of the date of onset of the adverse event is missing and it cannot be determined if the adverse event meets the definition for treatment-emergent.

The number and percentage of patients who experienced TEAEs for each system organ class and preferred term will be presented. Multiple instances of the TEAE in each system organ class and multiple occurrences of the same preferred term are counted only once per patient. The number and percentage of patients with at least one TEAE will also be summarized.

14 of 17

Separate tables will be presented as follows:

- All TEAEs;
- TEAEs by CTCAE grade;
- Grade 3 or greater TEAEs;
- Treatment-related TEAEs;
- Serious TEAEs (SAE);
- Serious treatment-related TEAEs;
- TEAEs with an outcome of death;
- TEAEs leading to discontinuation of study medication; and
- TEAEs resulting in reduction, delay, or interruption of study medication.
- Time to the first adverse events that results in a reduction, delay, interruption or discontinuation of study drug.

The incidence of TEAEs will be summarized by relationship to study drug according to the following categories: "treatment-related," or "not treatment-related". The category of treatment-related is defined as a relationship of "Possible/Probable", "Definitely", or missing. If a patient experiences multiple occurrences of the same AE with different relationship categories, the patient will be counted once, as a relationship category of treatment related.

If a patient experiences multiple occurrences of the same AE with different toxicity grades, the patient will be counted once for the maximum (most severe) toxicity grade. AEs with a missing toxicity grade will be presented in the summary table with a toxicity grade of "Missing." For each toxicity grade, the number and percentage of patients with at least one TEAE of the given grade will be summarized.

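### Adverse event percentages tabulated by dose and T790M status use patient-specific windows, so later-onset events are not comparable side by side if time on treatment differs

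*Protocol*

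**What the plan says.** Protocol 11.2.5.2 sets the window: "onset date on or after the date of first dose of CO-1686 until the date of the last CO-1686 dose plus 28 days". The measure is a proportion in which each patient counts once: "The number and percentage of patients who experienced treatment-emergent AEs for each SOC and PT will be presented". SAP 11.1 uses the same window and measure. Treatment runs until progression or unacceptable toxicity (Protocol 5.1.2), so the length of the window depends on how the patient fares.

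The split by group comes from the general conventions in Protocol 11.2.1: "Data will be summarized by T790M status and by dose, but may also be pooled as appropriate". Section 11.2.5.2 adds no contrast or test of its own.

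Cohort A is T790M-positive and starts at 625 mg BID; Cohort B starts at 500 mg BID (Protocol 5.1). On Cohort B, Protocol 6.1 says: "Cohort B: Approximately 100 patients will be enrolled in order to include approximately 40 response evaluable, centrally confirmed T790M-negative patients". T790M-positive patients enter Cohort B only once Cohort A is full.

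Exposure is tabulated separately (Protocol 11.2.5.1, SAP 7) and is not used as a denominator for events. SAP 11.1 and 11.2 do plan two censored time-to-first-event summaries: adverse events leading to dose change or discontinuation, and glucose above 13.875 mmol/L.

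**The concern.** Safety is a secondary objective, and Protocol 3.5 says the 500 mg data are meant to describe risk and benefit across the dose range. Safety tables by dose and T790M status will be read side by side for that purpose, with or without a test.

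A crude percentage answers how many patients had an event while they happened to be watched. If one group stops earlier, it has less time in which to show later events. A gap that comes only from time on treatment could then be read as a dose effect or a mutation-status effect.

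Because every T790M-negative patient is in the 500 mg cohort, a by-dose table that is not also split by T790M status carries any mutation-related difference in treatment duration into the apparent dose difference.

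**Working it through.** The plan states no adverse event rate and no treatment duration by group, so there is no figure to reproduce. What follows is an illustration.

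**Inputs from the documents.** A 28-day tail after last dose (Protocol 11.2.5.2), which is 28/30.4375 = 0.92 months. Hyperglycemia generally within the first 3 weeks (7.4). QTc prolongation typically evident by Day 15 (3.4.1.1). About 40 T790M-negative among about 100 Cohort B patients (6.1).

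**Assumptions.** Exponential time on drug with median m months, so μ = ln 2/m; medians 6 vs 4 up to 9 vs 3; the same constant event hazard λ per month in both groups.

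**Step 1, crude percentage.** P = 1 − exp(−0.92λ) × μ/(μ+λ), with λ chosen so that the longer-treated group shows 20%.
- 6 vs 4 months: λ = 0.0255. Longer group: 1 − 0.9768 × 0.1155/0.1411 = 20.0%. Shorter group: 1 − 0.9768 × 0.1733/0.1988 = 14.9%.
- 9 vs 3 months: λ = 0.0177. Longer group: 1 − 0.9838 × 0.0770/0.0947 = 20.0%. Shorter group: 1 − 0.9838 × 0.2310/0.2487 = 8.6%.

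The relative loss is smaller for common events. At 6 vs 4 months a 50% event (λ = 0.096) shows as 1 − 0.9155 × 0.1733/0.2693 = 41%.

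**Step 2, early-onset events.** Let a 30% risk act only during the first 21 days on drug, so λ = −ln(0.7)/21 per day and P = λ/(λ+μ) × (1 − exp(−21(λ+μ))), with μ per day. The result is 28.9% vs 28.4% at medians of 6 vs 4 months, and 29.3% vs 27.9% at 9 vs 3. The distortion is at most about 1.4 points.

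**Step 3, mixing of dose and mutation status.** Suppose dose has no effect, only T790M-negative patients stop sooner, and they are 40 of 100 in Cohort B. A 20% event at 625 mg then shows at 500 mg as 0.6 × 20 + 0.4 × 14.9 = 18.0% (6 vs 4 months) or 0.6 × 20 + 0.4 × 8.6 = 15.4% (9 vs 3).

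**Step 4, what common time points do.** With the end of the window as a competing event, the cumulative incidence at t is F(t) = 1 − exp(−0.92λ) × [μ/(μ+λ) × (1 − exp(−(μ+λ)s)) + exp(−(μ+λ)s)], where s = t − 0.92. Twelve weeks is 2.76 months (s = 1.84) and 24 weeks is 5.52 months (s = 4.60). Using λ from Step 1:

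| Medians (months) | Crude | By 12 weeks | By 24 weeks |
|---|---|---|---|
| 6 vs 4 | 20.0% vs 14.9% | 6.4% vs 6.2% | 10.8% vs 9.8% |
| 9 vs 3 | 20.0% vs 8.6% | 4.6% vs 4.2% | 8.1% vs 6.4% |

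The gap shrinks sharply but does not vanish by 24 weeks.

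**Step 5, why patient-time rates should not lead.** Give both groups an identical 30% early risk with mean onset near 10 days (0.33 months). Mean window length is m/ln 2 + 0.92, which is 9.58 months for a median of 6 and 6.69 for a median of 4. Time at risk per patient is 0.30 × 0.33 + 0.70 × 9.58 = 6.80 and 0.30 × 0.33 + 0.70 × 6.69 = 4.78 months. The rates are 30/6.80 = 4.4 and 30/4.78 = 6.3 per 100 patient-months, so the shorter-treated group looks worse at equal risk.

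**The case against.** The plan makes no formal comparison. The split is one general descriptive sentence, in a non-randomised Phase 2 study. That is correct, and the point is limited to how the tables will be read. Section 11.2.1 may already intend dose crossed with T790M status, but it does not say so and also allows pooling.

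A reader might infer that SAP 11.1 already makes the comparison. It does not: the SAP describes a single T790M-positive cohort of about 125 patients, with no Cohort B. Its two time-to-event summaries also answer part of the concern, but only for dose-modifying events and glucose.

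A reader might infer that the 500 mg or T790M-negative group will necessarily look safer. The early response rates in Protocol 3.4.2 (22 of 40, 55%, in T790M-positive patients; 36% of 11 in T790M-negative patients) make earlier stopping plausible in the latter but do not establish it. Several features could act in the other direction or blur the picture:
- Toxicity may shorten treatment at 625 mg.
- Cohort B excludes CNS metastases that Cohort A allows if treated and stable (6.3).
- Treatment may continue after progression (5.1.2).
- Fatal progression is recorded as a Grade 5 serious event (10.3).
- Later enrolment in Cohort B shortens its windows at an interim cutoff, but not once every patient has completed the End-of-Treatment Visit.

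Table 3-2, where treatment-related hyperglycemia is 28.0% at 750 mg against 61.1% at 500 mg, might be read as the effect already at work. It comes from preliminary data in another study, gives no follow-up by dose, and concerns an early-onset event. Likewise, Appendix C Table 1 gives cataract counts without onset times, so it cannot show that they accrue late.

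Finally, the ratio of mean window lengths suggests losses from 30% (1 − 6.69/9.58) to 62% (1 − 5.25/13.90, for 9 vs 3 months). These are ceilings for rare events, not the change in the tabulated percentages.

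**Conclusion.** The point holds in a limited form. The tables by dose and T790M status are crude proportions over windows whose length depends on time on treatment. For events that occur later in treatment they cannot be compared side by side if that time differs between groups. Under the assumed constant hazard and medians, a 20% event shows as 14.9% to 8.6% in the shorter-treated group. In 40 patients that is about 8 expected against 6.0 to 3.4. Hyperglycemia and QTc prolongation, which appear within about 3 weeks, are little affected.

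Both the size and the direction rest on assumptions, because the documents give no duration by group. The mixing of dose with T790M status in an unsplit by-dose table follows from the design and needs no assumption about duration. This is a reporting weakness worth repairing, not evidence that any group's safety has been misstated.

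**What to change.** Keep the crude tables. In Protocol 11.2.5.2, and in any SAP version that covers Cohort B, add the cumulative incidence of first event at common times after first dose, for example 12 and 24 weeks:
- Censor ongoing patients at data cutoff. Treat death and the end of the window (last dose plus 28 days) as competing events.
- Do this for all treatment-emergent events, those of Grade 3 or greater, and the terms in Appendix C Table 1.
- Present it by dose and T790M status, and show 500 mg against 625 mg within T790M-positive patients.
- Give the number of patients still in the window at each time, because some difference remains when groups leave at different rates.

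Exposure-adjusted rates may be added for later-onset events, including those beyond 24 weeks. They should not be used for front-loaded events, which they distort (Working, Step 5).

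The cost is a few extra programmed tables from onset and dosing dates already collected, with no new visits. Precision will be low in about 40 T790M-negative patients: at 20% the standard error is √(0.2 × 0.8/40) = 6.3 points.

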11.2.5.3 Clinical Laboratory Evaluations

Clinical laboratory evaluations include the continuous variables for hematology, serum chemistry, and urinalysis. Laboratory values will be presented in International System of Units. The baseline laboratory value will be defined as the last value prior to or on the day of the first dose of PO CO-1686. The on-treatment period will be defined as the day after the first dose of PO CO-1686 to 28 days after the last dose of CO-1686. Laboratory values collected during the on-treatment period will be included in the summary tables. The laboratory values collected after the on-treatment period will only be presented in the data listings.

The summary of laboratory data will include descriptive statistics (N, mean, standard deviation, minimum, median, and maximum) of the maximum, minimum, and last value during the treatment period. Summaries using descriptive statistics of the change from baseline to the maximum, minimum, and last value during the on-treatment period will also be given. Separate listings will be produced for clinically significant laboratory abnormalities (i.e., those that meet Grade 3 or 4 criteria according to CTCAE).

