3.4.3 Pharmacokinetics of CO-1686 HBr

Study CO-1686-016

In healthy volunteers (study CO-1686-016), maximum concentration (C_{max}), and area under the curve from time zero to 24 hours (AUC_{0-24}) of CO-1686 increased with ascending single doses of CO-1686 HBr (50 mg to 1000 mg), with CO-1686 plasma levels increasing in a less than dose proportional manner above 125 mg.

The single-dose PK of CO-1686 HBr was compared in the fasted and fed state, and it was concluded that a high-fat meal increased the plasma drug concentrations from 3-12 hours postdose with a mean increase of 172% at C_{12h} (-22% to +400%) and a mean increase of 77% in

[figure not shown]
AUC₀₋₂₄ (+10% to 146%) with no change in elimination half-life ($T_{1/2}$); a slight mean increase of 12% in C_{max} was observed and a delayed time to C_{max} (T_{max}) was seen in a majority of subjects.

Six healthy subjects were dosed, in the fed state, with 500 mg BID CO-1686 HBr for 4 days. PK profiles of CO-1686 following morning and evening dosings were similar, with low intra subject variability (Day 1 and Day 4 comparison). There was no accumulation of CO-1686.

Study CO-1686-008

In the patient study (CO-1686-008), PK data following CO-1686 HBr salt administration were available from a total of 44 patients (4 started at 500 mg BID, 10 switched from CO-1686 free base to 500 mg BID CO-1686 HBr, 15 started at 625 mg BID, 9 started at 750 mg BID, and 6 started at 1000 mg BID). CO-1686 HBr showed increased absorption and thus, higher exposure than free base. The median T_{max} was 2 to 3.25 hrs. and $T_{1/2}$ ranged from 1.7 – 4.7 hours. Following CO-1686 HBr administration, exposure (measured as C_{max} and AUC₀₋₂₄) increased dose-proportionally from 500 mg to 1000 mg BID (Figure 3-3).

Figure 3-3: Individual CO-1686 AUC₀₋₂₄ on Day 1 Following 500 mg to 1000 mg CO-1686 HBr BID

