Thus a **high score for a functional scale** represents a *high / healthy level of functioning*, a **high score for the global health status / QoL** represents a *high QoL*, but a **high score for a symptom scale / item** represents a *high level of symptomatology / problems*.

The baseline QoL measurement will be defined as the last value prior to or on the day of the first dose of CO-1686. The on-treatment period will be defined as the day after the first dose of CO-1686 to 28 days after the last dose of CO-1686. QoL measurements collected during the on-treatment period will be included in the summary tables.

Evaluation of Symptoms

An improvement in symptoms will be defined as a ≥ 10 point decrease from baseline. A worsening in symptoms will be defined as a ≥ 10 increase from baseline. Patients with neither an increase nor a decrease will be considered stable. The frequency and percentage of patients categorized as an increase, stable, or decrease will be presented.

Time to Deterioration

The time to a worsening in symptoms will be computed as 1+ the number of days from the first dose of study drug to the first instance of a ≥ 10 point increase from baseline in symptoms.

The time to deterioration will be summarized using Kaplan-Meier methodology. Patients without a 10 point increase will be censored on their last evaluation.

Longitudinal Analysis

The summary of QoL data will include descriptive statistics (N, mean, standard deviation, minimum, median, and maximum) of the mean and/or percent change from baseline during the on-treatment period. Summaries using descriptive statistics of the change from baseline to each scheduled visit during the on-treatment period will be presented.

Graphical presentations may be used to present the mean changes over time.

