#### 2 OVERALL STUDY DESIGN AND OBJECTIVES

## 2.1 Trial Design and Study Procedures

This is a Phase 2, single arm, open-label, multicenter study evaluating the safety and efficacy of CO-1686 administered orally twice daily to patients with previously treated mutant EGFR NSCLC whose tumor harbors the T790M resistance mutation. The central laboratory will confirm that the patient's tumor harbors the T790M mutation using biopsy material obtained from either primary or metastatic tumor tissue within 28 days of dosing with study drug and after progression on EGFR directed therapy.

CO-1686 will be administered to patients twice daily. Patients will take CO-1686 with a meal or within 30 minutes after a meal. Treatment with CO-1686 is continuous. Each 28 day period of treatment will represent one cycle, with dosing initiated on C1 D1. No dose escalation beyond the starting dose is allowed.

Patients will undergo serial assessments for anti-tumor efficacy, drug safety, and patient reported outcomes (see Section 9 of the Protocol). Sparse blood sampling for population PK analyses will be conducted in all patients treated with CO-1686. Serial blood sampling for longitudinal quantitative assessment of ctDNA will be conducted. Central laboratories will be used for hematology and chemistry, as well as for ECG interpretation.

Tumor scans will be acquired by the investigative site and evaluated locally for patient treatment decisions; however, copies of tumor scans will be sent to a independent radiological review (IRR) vendor. Protocol-specified treatment will continue until there is RECIST or clinical tumor progression or unacceptable toxicity as assessed by the investigator. Following disease progression on CO-1686 and discontinuation of protocol-specified treatment, patients who provide additional consent will undergo tumor biopsy before subsequent-line therapy is initiated. After discontinuation of protocol-specified treatment, subsequent anticancer therapy will be recorded.

All patients should return to the clinic for end-of-study assessments 28 (±7) days after the last dose of oral CO-1686 has been administered. The trial will be completed when all cnrolled patients have discontinued treatment in this protocol and completed the end-of-study follow-up visit.

All patients will be followed at approximately two monthly intervals to monitor survival status and subsequent NCSLC cancer therapy until death or sponsor decision, whichever comes first.

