#### 3 GENERAL ANALYSIS CONVENTIONS

Quantitative variables will be summarized using descriptive statistics and may also be summarized categorically with frequencies and percentages. For variables registered on a continuous scale, the following will be presented: N, mean, standard deviation, median, minimum and maximum. Categorical variables will be presented using frequencies and percentages.

The Kaplan-Meier methodology will be used to summarize DR, PFS, and OS. If estimable, the 50th (median) together with a 95% Confidence Interval (CI) will be presented. The number of patients with events and the number of censored patients will also be presented.

All data will be used to their maximum possible extent but without any imputations for missing data.

Unless otherwise specified, baseline is defined as the last measurement on or prior to the first day of study drug administration.

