# 11.2 Clinical Laboratory Evaluations

In this study, blood will be sent for analysis to a central laboratory for all cycles Day 1 visits, in addition to collecting the local lab results. The focus of the report will be based on these central laboratory results for all summary tables. Listings will be presented with both the central and local lab results. In addition, since glucose is a laboratory variable of interest the analyses around glucose will include both the central laboratory results and the local laboratory results.

Clinical laboratory evaluations include the continuous variables for hematology, serum chemistry, and urinalysis. Laboratory values will be presented in Standard International units. The baseline laboratory value will be defined as the last value prior to or on the day of the first dose of oral CO-1686. The on-treatment period will be defined as the day after the first dose of

oral CO-1686 to 28 days after the last dose of CO-1686. Laboratory values collected during the on-treatment period will be included in the summary tables. The laboratory values collected after the on-treatment period will only be presented in the data listings.

The summary of laboratory data will include descriptive statistics (N, mean, standard deviation, minimum, median, and maximum) of the maximum, minimum, and last value during the treatment period by dose group and study phase. Summaries using descriptive statistics of the change from baseline to the maximum, minimum, and last value during the on-treatment period will also be given by dose group and study phase. Separate listings will be produced for clinically significant laboratory abnormalities (i.e., those that meet Grade 3 or 4 criteria according to CTCAE).

The time to first Glucose value > 13.875 mmol/L will also be summarized. The time to first occurrence of a glucose value > 13.875 mmol/L will be calculated as 1+ the number of days from study drug start date to the first date of the glucose value > 13.875 mmol/L. Patients who do not have an observed glucose value > 13.875 mmol/L will be censored on the date of their last visit or data cutoff date for ongoing subjects.

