#### 11.3 Vital Signs

The on-treatment period will be defined as the time from the first dose of study drug to 28 days after the last dose of study drug. Vital sign measurements collected during the on-treatment period will be included in the summary tables.

The summary of vital sign data will include descriptive statistics (N, mean, standard deviation, minimum, median, third quartile and maximum) of the maximum, minimum and last value during the on-treatment period. Summaries using descriptive statistics (N, mean, standard deviation, minimum, median and maximum) of the change from baseline to the maximum, minimum, and last value during the on-treatment period will also be given.

Graphs of the mean values over time may also be provided.

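### The on-treatment window closes at last dose + 28 days, inside the End-of-Treatment visit's day 21–35 allowance, so appointment date decides whether an off-drug reading is tabulated as the last on-treatment value

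*Protocol*

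**What the plan says.** **End of the window.** Protocol 11.2.5.3 defines the laboratory on-treatment period as "the day after the first dose of PO CO-1686 to 28 days after the last dose of CO-1686". Values inside it are tabulated. For later ones, "The laboratory values collected after the on-treatment period will only be presented in the data listings". Protocol 11.2.5.4 applies the same window and the same listings-only rule to vital signs. The Quality of Life part of Protocol 11.2.4.2 uses the same window and adds that "QoL measurements collected during the on-treatment period will be included in the summary tables". SAP 11.2 repeats the laboratory rule, with a window that runs from the day after the first dose of "oral CO-1686 to 28 days after the last dose of CO-1686". SAP 11.3 also stops vital signs at 28 days and tabulates only on-treatment values.

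**The visit.** SAP 2.1 calls for "end-of-study assessments 28 (±7) days after the last dose of oral CO-1686". Protocol 5.1.3, 9.3, 12.1 and Table 9-1 give the same allowance. Under Protocol 9.3 the visit collects hematology, fasting chemistry, vital signs and the quality-of-life questionnaires. Table 9-1 puts it in the post-treatment columns, not among the daily-dosing visits.

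**The summaries.** Laboratory values and vital signs are reduced to each patient's maximum, minimum and last value, and to the change from baseline to each.

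**Start of the vital-sign window.** SAP 11.3 states: "The on-treatment period will be defined as the time from the first dose of study drug to 28 days after the last dose". SAP 3 states that "baseline is defined as the last measurement on or prior to the first day of study drug administration". Protocol 11.2.5.4 starts the vital-sign window on the day after the first dose. Day 1 vital signs are taken before dosing (Protocol 9.2.1; Table 9-1, footnote c).

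**The concern.** The cutoff sits on the nominal day of a visit that may occur a week either side of it. Two patients who stop on the same day and attend eight days apart can be handled in opposite ways. One contributes an off-drug reading labelled as the last on-treatment value. The other contributes an earlier reading, normally taken on drug, and the End-of-Treatment result goes to a listing. The row that appears to describe patients at the end of treatment is then a blend whose proportions depend on scheduling. For quality of life, the only questionnaire scheduled after stopping enters or leaves the change tables on the same basis.

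At the other end of the window, the SAP departs from the protocol for vital signs and from its own laboratory section. SAP 12, which lists changes from the protocol analyses, does not mention this. Under a date-based derivation, the baseline reading would also be a candidate for the on-treatment maximum or minimum.

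**Working it through.** The plan gives no figure to reproduce. The check is date arithmetic plus one algebraic step.

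**1. Visit days against the cutoff.** Inputs: a visit at 28 ± 7 days after the last dose (Protocol 9.3, Table 9-1, SAP 2.1) and a cutoff at last dose + 28 days (Protocol 11.2.4.2, 11.2.5.3, 11.2.5.4; SAP 11.2, 11.3).

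- Permitted days: 28 − 7 = 21 to 28 + 7 = 35, so 35 − 21 + 1 = 15 days.
- Inside the window: days 21–28, so 28 − 21 + 1 = 8 days.
- Outside the window: days 29–35, so 35 − 29 + 1 = 7 days; 7/15 = 46.7% of permitted days.

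**2. From days to patients.** The documents give no visit timing, so any patient share is an assumption. Visits spread evenly over the allowance would put about 47% outside. Visits clustered on day 28, with weight on day d proportional to exp(−(d − 28)²/(2s²)) over days 21–35, give 40% outside for s = 2 and 45% for s = 5. Site habit could produce anything from 0% to 100%.

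**3. Effect on each summary.**

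| Summary | Visit on days 21–28 | Visit on days 29–35 |
|---|---|---|
| Last value, change to last (labs, vital signs) | End-of-Treatment reading, at least 21 days off drug | Earlier reading, normally on drug |
| Maximum, minimum (labs, vital signs) | Changed only if this reading is the extreme | On-drug extremes only |
| Quality-of-life change tables | Included | Left out |
| Grade 3/4 laboratory listings | Kept | Kept |

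One wording point limits the laboratory rows. For change from baseline, Protocol 11.2.5.3 and SAP 11.2 refer to the on-treatment period. For the raw values they refer to the treatment period, a term those sections do not define. If it means the treatment columns of Table 9-1, the raw-value rows exclude End-of-Treatment while the change rows may include it.

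**4. Vital-sign start day.** Let b be the predose Day 1 reading, taken as baseline, and x₁, …, x_k the later on-treatment readings.

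- Window from the day after first dose (Protocol 11.2.5.4): change to maximum = max(x₁, …, x_k) − b, which can be negative.
- Window from the date of first dose (SAP 11.3 read by date): change to maximum = max(b, x₁, …, x_k) − b = max(0, max(x₁, …, x_k) − b) ≥ 0. By the same step, change to minimum ≤ 0.

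The resulting shift depends on within-patient variability, which the documents do not give, so it is not quantified here.

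**The case against.** The strongest reply is that 28 days is a coherent limit. It matches the treatment-emergent adverse event window in Protocol 11.2.5.2 and SAP 11.1. On-drug extremes survive in the maximum and minimum, Grade 3/4 laboratory values have their own listings, and SAP 11.2 analyses time to first high glucose separately. This stands for maxima, minima and adverse events. It does not answer the last-value problem, because neither document has a rule that maps the End-of-Treatment visit.

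On the start day, SAP 11.3 can be read by clock time. A predose reading then precedes the window and there is no overlap. The SAP does not say which reading applies, so the double role is conditional. The wording difference from the protocol is not.

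A reader might infer more than the documents support:

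- **That tabulated glucose has recovered because the drug clears in hours.** The half-life that "ranged from 1.7 – 4.7 hours" in Protocol 3.4.3 is for CO-1686 itself. Protocol 7.4 attributes hyperglycemia to a metabolite, whose half-life is not given, and no document reports glucose recovery by days 21–28. What can be said is that the reading is off drug.
- **That a late questionnaire is lost from every analysis.** Time to deterioration in Protocol 11.2.4.2 does not restate the 28-day limit. Appendix C, Table 4 schedules no further questionnaires, and SAP 12 defers quality of life from the NDA version.
- **That 47% of patients are affected.** It is a share of calendar days. At the NDA data cutoff, patients still on treatment have no End-of-Treatment visit.

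**Conclusion.** The inconsistency holds on the text. The cutoff at last dose + 28 days divides the visit allowance 8 days to 7, with no mapping rule. Last-value and change-to-last summaries therefore mix on-drug and off-drug readings by appointment date, and the quality-of-life change tables include or omit the End-of-Treatment questionnaire in the same way. The number of patients affected cannot be derived from the documents.

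The SAP's vital-sign start day conflicts with Protocol 11.2.5.4 and with the SAP's own laboratory window. If windows are applied by date, change to maximum cannot fall below 0 and change to minimum cannot rise above 0.

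Severity is minor. These are descriptive tables in a single-arm study, and the primary endpoint is not touched. The conclusion does not extend to the ECG summaries, which refer to treatment period visits without the 28-day definition.

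**What to change.** - **(a)** In Protocol 11.2.4.2, 11.2.5.3 and 11.2.5.4 and SAP 11.2 and 11.3, tabulate the End-of-Treatment visit as its own row, whatever its day within 21–35.
- **(b)** Define the last on-treatment value as the last value from a Treatment Period visit in Table 9-1, excluding End-of-Treatment. In Protocol 11.2.5.3 and SAP 11.2, use the term on-treatment period throughout, including for the raw-value summary.
- **(c)** Start the SAP 11.3 vital-sign window on the day after the first dose, as Protocol 11.2.5.4 and SAP 11.2 already do.

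Leave the 28-day limit in place for maximum and minimum, in line with the treatment-emergent adverse event window. The cost is wording and derivation code, with no new data.
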